## 7.0 METHODS OF ANALYSIS AND PRESENTATION

### 7.1 General Principles

All confidence intervals (CI), statistical tests, and resulting P-values will be reported as 2-sided and will be assessed at  $\alpha=0.05$  significance level unless otherwise stated. P-values will be rounded to 3 decimal places prior to assessment of statistical significance.

Means and medians will be presented to 1 more decimal place than the recorded data. The standard deviations (SDs) will be presented to 2 more decimal places than the recorded data. Confidence intervals about a parameter estimate will be presented using the same number of decimal places as the parameter estimate.

Where appropriate, variables will be summarized descriptively by study visit. For the categorical variables, the counts and percentages of subjects will be tabulated. The denominator for the percentages will be based on the number of subjects who provide non-missing responses to the categorical variable. For continuous variables, the number of subjects with non-missing values, mean, median, SD, minimum, and maximum values will be tabulated.

All data analyses and figures will be generated using SAS System® Version 9.2 or higher.

#### 7.1.1 Definition of Study Day and Baseline

Study day will be calculated relative to the date of the first dosing. Study day prior to the first dose of treatment will be calculated as: date of assessment/event – date of treatment; study day on or after the date of first dose of treatment will be calculated as: date of assessment/event – date of treatment + 1.

Baseline for Part 1 is defined as the last non-missing measurement prior to first dose of study drug in Part 1. Baseline for Part 2 is defined as the last non-missing measurement prior to first dose of study drug.

Baselines for Part 1 and Part 2 (when needed for the analysis) are defined as the last observation prior to the first dose in Part 1 and 2, respectively. Both date and time of the measurement and the dosing date and time should be used when determining the baseline if possible. For Part 1, in the case where the last non-missing measurement (except AE and concomitant medications) and the first dose on Day 1 coincide at the same time, or the same date if time of the measurement is not collected, that measurement will be considered as baseline value for Part 1. For Part 2, in the case where the last non-missing measurement (except AE and concomitant medications) and the first dose on Day 31 coincide at the same time, or the same date if time of the measurement is not collected, that measurement will be considered as baseline value for Part 2.

#### 7.1.2 Definitions of Study Visit Windows

For each visit, a window will be defined; this window will establish a time interval around which data will be considered for the analysis of the scheduled visit pertaining to that window. The lower and upper bounds of each window are the approximate midpoints between the scheduled days for the current visit and its adjacent scheduled visits. The value used in analysis for by-visit

summaries is the value within the specified window that is closest to the scheduled study day. If two observations are equidistant from the scheduled visit date, the observation with a later date will be used. The visit windows and applicable study day ranges are presented below in [Table 7.a](#) and [Table 7.b](#). Cut-off days for inclusion in the window (number of days following the date of the last dose of open-label study drug) are provided.

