Seizure data will be recorded daily in the seizure diary by each subject and/or subjects' caregiver throughout the Screening/Baseline Period up until the Follow-up Visit (Visit 9) on Day 121 and will be collected from the diary at each visit.

The investigator, in consultation with the sponsor, may decide to reduce the TAK-935 dose at any time during the study in the event of any safety or tolerability concerns.

Any subject who prematurely withdraws from the study should proceed directly to the Final Visit (at time of withdrawal), including dose de-escalation, as appropriate, followed by the 30-day Follow-up Period.

A schematic of the study design is shown in [Figure 6.a](#). A schedule of study procedures is listed in [Appendix A](#).

Figure 6.a Schematic of Study Design

Note 1: Circled numbers denote study visits.

Note 2: Subjects will remain on stable background AED therapy throughout the study.

Note 3: Starting doses for Parts 1 and 2 are shown; individual subject doses may be reduced to the previous dose level if there are safety and tolerability concerns at new dose level.

Note 4: Maintenance dose levels (ie, 100, 200, or 300 mg BID) will be de-escalated at the end of the maintenance phase of Part 2, depending on the dose subjects are taking at that time (ie, if at TAK-935 300 mg BID level, reduce to 200 mg BID for 3 days followed by 100 mg BID for 3 days; if at the 200 mg BID level, reduce to 100 mg BID for 3 days; if at the 100 mg BID level, there is no de-escalation).

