**Table 7.a Visit Analysis Windows for Part 1**

Visit	Scheduled Visit Day	Visit Window (Days)				
		Vital Signs, CCI, PK, CC Plasma Sample for AED, Concomitant Medications	CCI	ECG, Clinical Laboratory Tests	CCI, Serum/urine Pregnancy Test	Physical Exam, Neurological Exam
Baseline I	1	≤1	≤1	≤1	≤1	≤1
Visit 3	11	2-16	2-16	2-16	2-43	
Visit 4	21	17-26	17-26			2-33
Visit 5	31	27-36	27-36	17-58		
Visit 6	41	37-53	37-53			
Visit 7	85	54-Last Dose+7	54-Last Dose+7	59-Last Dose+7	44-Last Dose+7	34-Last Dose+7

Note: Any value collected after the administration of first dose on Day 1 will be grouped under Day 2, except for PK, CCI and plasma sample for AED.

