**Table 7.b Visit Analysis Windows for Part 2**

Visit	Scheduled Visit Day	Visit Window (Days)				
		Vital Signs, CCI, PK, C, Plasma Sample for AED, Concomitant Medications	CCI	ECG, Clinical Laboratory Tests	CCI, Serum/urine Pregnancy Test	Physical Exam, Neurological Exam
Baseline II		≤First Dose in Part 2	≤First Dose in Part 2	≤First Dose in Part 2	≤First Dose in Part 2	≤First Dose in Part 2
Visit 6	41	Day after First Dose in Part 2-53	Day after First Dose in Part 2-53			
Visit 7	85	54-Last Dose+7	54-Last Dose+7	Day after First Dose in Part 2-Last Dose+7	Day after First Dose in Part 2-Last Dose+7	Day after First Dose in Part 2-Last Dose+7

Note: Any value collected after the administration of first dose in Part 2 will be grouped under day after first dose in Part 2, except for PK, CCI and plasma sample for AED.

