### 7.11.3 Vital Signs

Descriptive statistics (N, mean, SD, median, minimum, and maximum) will be used to summarize vital sign parameters at baseline, each post-baseline visit, and change from baseline to each post-baseline visit for both Parts 1 and 2. Study baseline defined in Section 7.1.1 will be used. Only observations within 7 days of the study drug will be included in the tables.

Vital sign MAVs, identified by the criteria defined in [Appendix B](#), will be tabulated. If a subject has a MAV for a particular vital signs parameter, all visits for that subject for that parameter will be listed. The number and percentage of subjects with at least 1 post-dose markedly abnormal vital signs measurement will be summarized. The mapping of the subjects who meet the MAV criteria will be listed as a table. All observations, including ones at unscheduled visits, will be included in the MAV evaluation and summaries if MAV criteria are satisfied.

All vital signs will be listed in a data listing.

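### By-visit vital-sign tables can leave out the Final Visit value of a subject who withdraws soon after an up-titration visit, and no other table row holds it

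*SAP*

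**What the plan says.** SAP 7.1.2 assigns measurements to visits by study day and then picks one per window. For by-visit tables, the value used in these "summaries is the value within the specified window that is closest to the scheduled study day". On ties: "If two observations are equidistant from the scheduled visit date, the observation with a later date will be used". On the limits of each window: "The lower and upper bounds of each window are the approximate midpoints between the scheduled days".

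For vital signs, Table 7.a sets Days 2-16 for Visit 3 (Day 11), then "Visit 4 21 17-26", Days 27-36 for Visit 5, and "Visit 6 41 37-53". In Table 7.b the Part 2 window for Visit 6 is "Day after First Dose in Part 2-53". In both tables the Visit 7 (Final Visit) window opens on Day 54.

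Protocol 6.1 states: "Any subject who prematurely withdraws from the study should proceed directly to the Final Visit (at time of withdrawal"). The Final Visit of an early withdrawal is therefore not tied to Day 85.

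SAP 7.11.3 summarises vital signs at baseline, "each post-baseline visit, and change from baseline to each post-baseline visit for both Parts 1 and 2". It has no row for early termination, last on-treatment value or worst value. The same section takes all observations, including unscheduled ones, into the MAV evaluation and lists all vital signs.

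**The concern.** The planned dose increases are on Days 11, 21 and 41, which are also clinic visits with vital signs. A subject who withdraws in the days after such a visit has two values in one window. One comes from the day of the increase. The other is the Final Visit value, taken after one or more days on the new dose unless it was reduced in between. The nearest-day rule generally keeps the first.

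For a subject raised to 300 mg BID on Day 21 who withdraws on Days 22-26, there is no later Visit 5 value either. The by-visit table then holds no scheduled vital sign for that subject after days on 300 mg BID. Protocol 13.1.3.2 promises changes from baseline by part, and safety and tolerability is the primary objective. At stake is whether the descriptive vital-sign tables show the last on-treatment value of the subjects who stopped.

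**Working it through.** **Inputs.** Scheduled days 11, 21, 31, 41, 85 and the ±2-day visit allowance (Protocol Appendix A); windows (SAP Tables 7.a and 7.b); closest-value and tie rules (SAP 7.1.2); Final Visit at withdrawal (Protocol 6.1).

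**Step 1: reproduce the windows.** Midpoints of adjacent vital-sign visits: (11+21)/2 = 16, (21+31)/2 = 26, (31+41)/2 = 36, all as in Table 7.a. For Visit 6, (41+85)/2 = 63, but both tables give 53. That is a separate inconsistency; the steps below use the stated 53.

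**Step 2: up-titration visit on its scheduled day.** Its distance from the scheduled day is 0, so any later value in the same window loses.
- After Day 11: Days 12-16 dropped (16 − 11 = 5 days).
- After Day 21: Days 22-26 dropped (26 − 21 = 5 days).
- After Day 41: Days 42-53 dropped (53 − 41 = 12 days). With an upper bound of 63 this would be Days 42-63 (22 days).

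**Step 3: visits moved by up to ±2 days.** Let T be the scheduled day, v the actual visit day and w the Final Visit day, with w = v+1 to v+5. The Final Visit value is dropped if w lies in the same window and |w − T| > |v − T|; a tie goes to the later value.

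| Actual visit day | T−2 | T−1 | T | T+1 | T+2 | Total |
|---|---|---|---|---|---|---|
| Visits 3 and 4: dropped of 5 | 1 | 3 | 5 | 4 | 3 | 16 of 25 |
| Visit 6: dropped of 5 | 1 | 3 | 5 | 5 | 5 | 19 of 25 |

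Two examples that are kept: Visit 3 on Day 9 with a Final Visit on Day 13 ties at 2 days, so the later value is used; Visit 3 on Day 13 with a Final Visit on Day 17 falls into two windows. Also, a Part 2 subject who withdraws before Visit 6 has the Final Visit as the only scheduled value in the Table 7.b Visit 6 window, so it is shown.

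**Step 4: what the retained value represents.** Protocol 9.1.18.1 gives the clinic dose immediately after the predose sample, and Protocol 9.1.6 places vital signs within 0.25 hour of a draw scheduled at the same time. Days 11 and 21 also have a draw about 1 hour after the dose. If vital signs go with a scheduled draw, the retained value was taken before the first higher dose or about an hour after it. It does not reflect days on the new dose.

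**Step 5: where the dropped value still appears.** In the MAV evaluation and the listing (SAP 7.11.3). The 7-day cut-off does not remove it. The MAV limits in SAP Appendix B are absolute, with no change-from-baseline criterion. As an illustration, systolic pressure going from 130 to 95 mm Hg changes by 35 mm Hg but is not a MAV, because the lower limit is <85. Only the change-from-baseline table would summarise it, and there it is dropped.

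**The case against.** The strongest case against is that nothing defined as an endpoint in the readable text is touched. The primary endpoint is TEAEs. The vital-sign secondary endpoint is the percentage of subjects with at least one MAV, which uses all observations. TEAEs leading to discontinuation, reasons for discontinuation and dose sequences are reported separately, and with about 20 subjects the full listing can be read line by line. Closest-to-target selection also has a purpose: it keeps a Visit 3 row describing Visit 3. All of this stands, and it limits the point to descriptive tables.

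The design also weakens the idea that these days are when intolerance leads to withdrawal. Protocol 6.1 allows a reduction to the previous level for subjects who do not tolerate 200 or 300 mg BID, and ties required withdrawal for intolerance to 100 mg BID. Withdrawal after a step-up remains possible under Protocol 7.5, but it is not the only planned response.

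The scope is narrow too. In the ECG and laboratory column of Table 7.a, a Part 1 withdrawal value normally has no competing scheduled post-baseline value in its window and is kept.

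What the objection does not remove is that a stated selection rule drops the last on-treatment value from the change-from-baseline summary, as a side effect of where the windows end. With Visits 3 and 4 on schedule, a Final Visit on Day 17 is shown and one on Day 16 is not.

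**Conclusion.** The point holds for the by-visit and change-from-baseline vital-sign tables only. With on-schedule visits, Final Visit values on Days 12-16, 22-26 and 42-53 are left out. With ±2-day visits and a Final Visit 1-5 days later, 16 of 25 combinations are dropped at Visits 3 and 4 and 19 of 25 at Visit 6. These are counts of day combinations, not probabilities. It is a cheap improvement, not an error that threatens a study conclusion.

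A reader might infer more, and the documents do not support it:
- *That the tables are biased toward tolerability.* No expected direction of vital-sign change is given, so the direction is unknown.
- *That the values are lost to the analysis.* The MAV evaluation and listings keep them.
- *That the share of affected days measures the effect.* In Part 1 it is 10 of 27 non-visit days (Days 2-30 without 11 and 21), but no withdrawal rate is given, so the number of subjects cannot be estimated. An affected subject also still contributes a value to the row.
- *That the retained value is always pre-escalation.* The timing of vital signs relative to the dose is not fixed.
- *That plasma AED results suffer in the same way.* They share the window column, but their analysis section is redacted and cannot be judged.

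**What to change.** In SAP 7.1.2 and 7.11.3, add one row per study part for the *last on-treatment value*: the last observation in that part up to last dose + 7 days, with its change from baseline. For subjects who continue, the Part 1 row should stop at the first Part 2 dose, using the Day 31 convention in SAP 7.1.1. Leave the scheduled-visit rows and the closest-value rule as they are.

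The cost is a few lines of SAP text and one extra row per part in the vital-sign tables. The data are already collected, and trial conduct does not change. The downside is that the row pools subjects at different doses and treatment durations, so its label should say so.

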**Table 7.a Visit Analysis Windows for Part 1**

Visit	Scheduled Visit Day	Visit Window (Days)				
		Vital Signs, CCI, PK, CC Plasma Sample for AED, Concomitant Medications	CCI	ECG, Clinical Laboratory Tests	CCI, Serum/urine Pregnancy Test	Physical Exam, Neurological Exam
Baseline I	1	≤1	≤1	≤1	≤1	≤1
Visit 3	11	2-16	2-16	2-16	2-43	
Visit 4	21	17-26	17-26			2-33
Visit 5	31	27-36	27-36	17-58		
Visit 6	41	37-53	37-53			
Visit 7	85	54-Last Dose+7	54-Last Dose+7	59-Last Dose+7	44-Last Dose+7	34-Last Dose+7

Note: Any value collected after the administration of first dose on Day 1 will be grouped under Day 2, except for PK, CCI and plasma sample for AED.

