Part 2 of the study is designed to investigate the safety, tolerability, PK, and PD of TAK-935 in adult subjects with developmental and/or epileptic encephalopathies in an open-label manner. All subjects who complete the Double-Blind Treatment Period in Part 1 will have the option to continue directly into the Open-Label Treatment Period in Part 2. Because some subjects may enter Part 2 after receiving placebo and others TAK-935 up to 300 mg BID and to maintain the study blind, all subjects will start on TAK-935 200 mg BID at the start of Part 2. On Day 31 (Visit 5), subjects will return to the clinic and receive TAK-935 200 mg BID from Days 31 to 40 but may be reduced to 100 mg BID in subjects who cannot tolerate the 200 mg BID dose or demonstrate safety concerns, based on the investigator's judgment and in consultation with the subject's caregiver, when applicable. Subjects who cannot tolerate the 100 mg BID dose or demonstrate safety concerns, based on the investigator's judgment and in consultation with the subject's caregiver, will be discontinued from the study. On Day 41 (Visit 6), subjects will return to the clinic; at this visit, the investigator will review the subject's safety data and will discuss the benefit-risk with the subject or subject's legally acceptable representative before proceeding to increase the dose from 200 mg BID to 300 mg BID, and this dose level will be maintained until the Final Visit (Visit 7) for the dose de-escalation phase. Subjects' dose may be increased or decreased before Day 41 (Visit 6) based on clinical condition (ie, increasing seizures) and investigator judgment. This dose may be reduced to 200 mg BID in subjects who cannot tolerate the 300 mg BID dose or demonstrate safety concerns, as described above. Subjects for whom the dose was reduced to a lower dose level will stay on that dose level until the Final Visit (Visit 7) for the dose de-escalation phase. Three days after each dose up-titration or de-escalation, subjects will be contacted by phone to monitor study drug compliance, concomitant medication use, and AEs. Any change in dose will be documented in the subject's clinic chart and the subject's caregiver will be advised to note the same in the dosing card.

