## 7.11 **Safety Analysis**

Safety analyses include AEs, clinical laboratory parameters, vital sign parameters, 12-lead ECG results, and other safety parameters. The safety analysis set will be used for all summaries of safety parameters. The safety endpoints will be presented by placebo TAK-935, and overall in Part 1, by placebo, TAK-935 received in Part 1 and overall in Part 2 of the study, and by placebo, TAK-935 received in Part 1 and overall for Part 1 and 2 combined.

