**Diagnostic Screening**

Serum	Urine (a)
HIV	Drug screen including amphetamines, barbiturates,
HBsAg and anti-HCV	benzodiazepines, cannabinoids, cocaine, opiates, alcohol, and
HCV RNA detection by qPCR (e)	cotinine
hCG (for pregnancy) (f)	hCG (for pregnancy) (f)

aPTT= activated partial thromboplastin time, FSH=follicle-stimulating hormone, GGT=γ-glutamyl transferase, HDL=high-density lipoprotein, LDL=low-density lipoprotein, PT=prothrombin time, RBC=red blood cell; WBC=white blood cell.

(a) If urine cannot be collected at the time of the Screening Visit or other Visits due to the subject's cooperation or because the subject is wearing a diaper, it is acceptable for the subject to continue in the study and the reason should be documented in the source document.

(b) Only if dipstick results are positive.

(c) For diagnostic purposes in female subjects only.

(d) In female patients only

(e) Subjects who are positive for hepatitis C Ab should return to the clinic for an unscheduled visit to provide a blood sample for HCV qPCR.

(f) Only for female subjects of childbearing potential. If urine cannot be collected at Visit 2, the reason should be documented in the source document and the results of the serum pregnancy test obtained at Visit 1 must be confirmed to be negative by the investigator prior to randomization. An additional serum hCG pregnancy test will be performed at the Final Visit.

All laboratory test parameters will be displayed in individual subject data listings in both SI units and conventional (CV) units. For test results not in SI units, the conversion to SI units will be done in derived analysis data sets using the known conversion factors. If necessary, SI units from the central laboratory may be converted to Takeda's preferred SI units in the derived dataset. All summaries and analyses will be based on the values using these preferred SI units.

Only observations within 7 days of the last dose of study drug will be included in the tables. No inferential statistics will be presented unless otherwise stated.

Descriptive statistics (N, mean, SD, median, minimum, and maximum) for the observed and change from baseline values will be presented for Parts 1 and 2 separately. Study baseline defined in Section 7.1.1 will be used for change from baseline in each part of the study. Note that character urinalysis tests will only be listed.

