### 7.11.4 12-Lead ECGs

Descriptive statistics (N, mean, SD, median, minimum, and maximum) of ECG parameters, including heart rate, PR interval, RR interval, QRS interval, QT interval, and QTc interval (Fredericia's and Bazett's corrections), will be presented for baseline, each post-baseline visit, and change from baseline to each post-baseline visit for both Parts 1 and 2. Study baseline defined in Section 7.1.1 will be used. Only the scheduled measurements will be included in the

summary. Only observations within 7 days of the study drug will be included in the tables. No inferential statistics will be presented.

ECG MAVs, identified by the criteria defined in [Appendix C](#), will be tabulated. If a subject has a MAV for a particular 12-lead ECG parameter, all visits for that subject for that parameter will be listed. The number and percentage of subjects with at least 1 post-dose markedly abnormal 12-lead ECG measurement will be summarized. The mapping of the subjects who meet the MAV criteria will be listed as a table. All observations, including ones at unscheduled visits, will be included in the MAV evaluation and summaries.

Overall ECG interpretation category (normal, abnormal not clinically significant, abnormal clinically significant, not evaluable) is collected by eCRF at baseline and at each scheduled post-baseline visit. Shifts in ECG interpretation will be presented as cross-tabulations (baseline versus each post-baseline visit) of numbers of subjects with normal, abnormal not clinically significant, and abnormal clinically significant interpretations, not evaluable, with missing, if applicable, and total categories by each treatment (placebo, TAK-935).

All ECG parameters will be listed in a data listing.

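### SAP Table 7.a carries the Part 1 by-visit windows into open-label treatment, so the Day 41 and Day 85 rows label former placebo subjects on TAK-935 as placebo

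*SAP*

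**What the plan says.** - **Windows.** SAP Section 7.1.2 assigns each value to a visit by study day. The table headed "Table 7.a Visit Analysis Windows for Part 1" starts at Baseline I and goes on to Visit 6 (Days 37-53 for vital signs) and Visit 7 (from Day 54 for vital signs, Day 59 for ECG and laboratory tests, to Last Dose+7).
- **Cut-off.** The same section says: "Cut-off days for inclusion in the window (number of days following the date of the last dose of open-label study drug) are provided". The late windows are therefore tied to the open-label last dose, not to the last Part 1 dose.
- **Treatment.** Part 1 is 30 days of double-blind dosing. For those who continue, SAP Section 4.4 says "all subjects will start on TAK-935 200 mg BID at the start of Part 2", which is Day 31.
- **Displays.** SAP Section 7.11: "The safety endpoints will be presented by placebo TAK-935, and overall in Part 1". Its Part 2 and combined displays are grouped by the treatment received in Part 1. Section 7.11.2 says that laboratory observed and "change from baseline values will be presented for Parts 1 and 2 separately". Sections 7.11.3 and 7.11.4 summarise vital signs and ECGs at each post-baseline visit for both parts. Section 7.11.4 also cross-tabulates ECG interpretation at each post-baseline visit under placebo and TAK-935.
- **Part 2.** Table 7.b covers Visits 6 and 7 again, measured from Baseline II.

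**The concern.** Placebo is the only concurrent control for laboratory, vital-sign and ECG changes, and it exists only up to the first Part 2 dose. A programmer who applies Table 7.a as titled will print Day 41 and Day 85 rows in the Part 1 tables. The former placebo subjects in those rows are taking TAK-935, but the column heading still reads placebo. A real drug effect on QTcF, liver enzymes or blood pressure could then appear in both columns and be read as no difference from placebo. The issue is which treatment the control column represents at those visits. It is not a question of which baseline is subtracted.

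**Working it through.** **1. Reproducing the plan's bounds.** The rule is that "bounds of each window are the approximate midpoints between the scheduled days for the current visit and its adjacent scheduled visits", so each bound should be (a + b)/2 for adjacent scheduled days a and b.

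| Column | Adjacent days | (a + b)/2 | Upper bound in Table 7.a |
|---|---|---|---|
| Vital signs | 11, 21 | 16 | 16 |
| Vital signs | 21, 31 | 26 | 26 |
| Vital signs | 31, 41 | 36 | 36 |
| Vital signs | 41, 85 | 63 | 53 |
| ECG/laboratory | 1, 31 | 16 | 16 |
| ECG/laboratory | 31, 85 | 58 | 58 |
| Pregnancy test | 1, 85 | 43 | 43 |
| Physical/neurological exam | 21, 85 | 53 | 33 |

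Two bounds (53 and 33) do not follow the rule. Neither changes the conclusion below, but both should be checked.

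**2. Scheduled visits affected** (protocol Appendix A, on-treatment, post-baseline).
- Vital signs: Days 11, 21, 31, 41 and 85. Days 41 and 85 follow the first open-label dose: 2 of 5.
- ECG and laboratory tests: Days 31 and 85. Day 85 follows it: 1 of 2.

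**3. Can a subject who never enters Part 2 fill the late rows?** The latest last dose for such a subject is Day 30 + 6 de-escalation days = Day 36. Adding 7 days gives Day 43, or about Day 45 with the +2-day visit window. The Visit 7 window opens on Day 54 (vital signs) or Day 59 (ECG/laboratory), so for those measures it can hold Part 2 data only. The same is not true of every column. Visit 7 opens on Day 34 for physical and neurological examinations and on Day 44 for pregnancy tests, and the vital-sign Visit 6 window opens on Day 37, so a value from a Part 1-only subject could fall there.

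**4. Share of window time.** Take a placebo subject who continues and has the last dose on Day 90. The windows cover Days 2 to 97 = 96 days. Days 31 to 97 = 67 of them (67/96 = 70%), made up of 60 days on open-label drug and 7 after it. With the last dose on Day 85 the figure is 62/91 = 68%. This is calendar space, not a count of data values.

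**5. Effect on the Day 85 contrast.** Before the Day 85 visit, former placebo subjects have had Days 31-84 = 54 days of TAK-935. Let d be the drug effect in the TAK-935 column, and suppose former placebo subjects show a fraction f of it. The displayed difference is d - f x d = (1 - f)d. The documents give no value for f. With f = 0, 0.5 and 1 the difference is d, 0.5d and 0.

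**6. Visit 5, ECG and laboratory.** The window is Days 17-58 = 42 days, of which Days 31-58 = 28 lie on or after the nominal open-label start. But the value used "is the value within the specified window that is closest to the scheduled study day", so a Day 31 value always wins, and the Day 31 blood samples are taken before the dose. Appendix A schedules no ECG or laboratory test between Days 31 and 85. An open-label value can enter only when no Day 31 value exists and there is an early Final Visit on Days 32-58 or, for laboratory tests, an unscheduled draw.

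**The case against.** The strongest reply is that Table 7.a was meant for the combined Part 1 and 2 display. Section 7.11 lists that display, it needs windows from Baseline I through Visit 7, and no other table supplies them. On this view the title is too narrow and nobody would print Visits 6 and 7 in a Part 1 table. The table shells are not available and some analysis sections are redacted, so other uses of the table cannot be ruled out. This reading is plausible, but the SAP does not state it, and it would leave Part 1 with no window table at all. A correction is needed either way. The reply does defeat one remedy: deleting the late rows outright would take away the combined display's Baseline I windows.

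It is also fair that the late rows are identified by visit and not pooled with earlier ones, and that the SAP already groups its Part 2 and combined columns by Part 1 treatment. The Part 1 columns carry no such qualifier, so a reader would take placebo there to mean current treatment.

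**Conclusion.** The point holds on the text as written and should be corrected, but its reach is limited. It concerns the Visit 6 and 7 rows for vital signs, the Visit 7 row for laboratory tests and ECG, and the Day 85 ECG shift table. It involves at most about 4 planned placebo subjects, and only those who take up the optional Part 2.

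Three stronger readings are tempting and are not supported:
- **The whole Part 1 placebo column is contaminated.** Visits 3 and 4 fall on placebo, and the Day 31 blood samples are pre-dose. Those visits remain a valid contrast.
- **Visit 5 is mostly open-label because 28 of its 42 window days are.** The closest-value rule prevents this whenever a Day 31 value exists.
- **The primary or secondary safety endpoints are distorted.** TEAEs have their own time rule in Section 7.11.1. Markedly abnormal value counts in Sections 7.11.2 to 7.11.4 use all observations, including unscheduled ones. Table 7.a governs neither, and the affected laboratory, vital-sign and ECG summaries are descriptive.

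The conclusion assumes that Table 7.a is applied as titled. Complete loss of the Day 85 contrast further assumes that the effect has fully developed after 54 days (f = 1).

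**What to change.** 1. Retitle the current Table 7.a as the Baseline I windows for the Part 1 and 2 combined display.
2. Add a true Part 1 window table covering Visits 3 to 5. End every window at the earlier of the first Part 2 dose and last Part 1 dose + 7 days, and include early Final Visit values within that limit. For vital signs this gives Days 2-16, Days 17-26, and Day 27 to the limit. The ECG/laboratory Visit 5 window runs from Day 17 to the limit. For a continuing subject on schedule, the limit is the pre-dose Day 31 value. For a subject who stops, it is Day 30 + 7 = Day 37 if the last dose is on Day 30, or Day 36 + 7 = Day 43 after a 6-day de-escalation.
3. Report Days 41 and 85 only in the Part 2 and combined tables, with columns labelled placebo to TAK-935 and TAK-935 to TAK-935.
4. Apply the same limit and labels to the ECG shift table in Section 7.11.4.
5. While editing, check the 53/54 and 33/34 bounds against the midpoint rule.

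The cost is SAP wording, one extra window table and revised table shells. No new data or procedures are needed, and change from the pre-drug baseline at Day 85 stays visible in the combined tables.
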